7.2.4 Open-label Treatment Phase

The following procedures are to be completed during the open-label treatment phase at time points designated in the Schedule of Assessments ([Table 1](#)).

- Physical examination (including neurological examination) as per standard of care
- Weight
- Vital signs
- ECG
- Laboratory assessments using the central laboratory: urine drug screen (based upon the investigator's clinical suspicion), chemistry and hematology panels
- Urine pregnancy test
- PK sampling
- AMG 334 antibody collection
- COAs, migraine symptom interference items and PROMIS
- C-SSRS
- MSQ and MIDAS. The subject will complete these PROs while in the clinic, using the eDiary. For each study visit, these PROs should be completed prior to invasive procedures (eg, blood draws).

- Novel PRO Substudy: The MPFID (optional)
- Concomitant medications recording
- Serious and non-serious adverse event recording
- Subject brings eDiary to site
- Administration of AMG 334 70 mg or 140 mg SC QM. Administration of AMG 334 should be the last procedure performed at each study visit.
- Increase IP to 140 mg for subjects enrolled on 70 mg at first available opportunity at either week 4, 8, 12, 16, 20, 24 or 28 (during regular IP Assignment IVRS/IWRS call)
- CHU Substudy in US, Germany, and Sweden (optional)
 - After confirming the ICF has been signed, the following procedures are to be completed:
 - Screening (20130255 week 8 or 36): Review of IFU and RG for both PFS and **prefilled** Al/pen with subject
 - After confirming subject eligibility, the following procedures are to be completed:
 - Day 1 (20130255 week 12 or 40):
 - Randomization of the subject to PFS or **prefilled** Al/pen self-administration using the IVR/IWR System
 - Site to instruct subject on how to self-administer AMG 334 with either PFS or **prefilled** Al/pen by reviewing entire IFU and RG
 - Physical examination of subject with particular attention to any skin abnormalities in areas that might be used for IP self-administration
 - Subject self-administration using either PFS or **prefilled** Al/pen under site supervision
 - Review for ADEs, **adverse events, and serious adverse events**
 - Study Coordinator to reconcile IP (PFS or **prefilled** Al/pen)
 - Product Complaint Recording (if applicable)
 - Day 28 (20130255 week 16 or 44):
 - Study coordinator dispenses PFS or **prefilled** Al/pen to subject for self-administration on day 29

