10.1.2 Analysis Sets

The full analysis set (FAS) includes all subjects who were enrolled in the study and received at least one dose of investigational product. All subjects participating in the PRO substudy and have at least one monthly score for the MPFID will be included in the PRO analysis set. All subjects enrolled in the CHU substudy will be included in the CHU analysis set.

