10.4 Planned Methods of Analysis

10.4.1 General Considerations

All subjects who have received at least one dose of AMG 334 in the study will be included in the data analysis according to their allocated treatment groups in the parent study, as well as an overall analysis (of all subjects in the OLE study).

For the purpose of primary analysis for secondary and exploratory endpoints in the 20130255 OLE study, baseline is defined as baseline of the AMG 334 20120295 parent study (from the first day subject used eDiary in baseline at week -4 study visit through the day prior to study day 1). However, change from the parent study Month 3 data will also be evaluated.

Descriptive statistics will be presented for all endpoints. Summary statistics for continuous variables will include number of subjects, mean, median, standard deviation,

standard error, lower and upper quartiles, minimum, and maximum. For categorical variables, frequency and percentage will be given.

No formal statistical tests will be performed. Missing values for safety endpoints will not be imputed.

Subject disposition, demographics, and baseline characteristics will be summarized.

The full analysis set will be utilized to tabulate subject disposition of all enrolled subjects, the demographic data, baseline disease characteristics, efficacy, and safety endpoints.

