10.4.2 Efficacy Endpoint

Descriptive summaries on efficacy endpoints will be provided by treatment group of the AMG 334 20120295 parent study (ie, AMG 334 70 mg, AMG 334 140 mg), treatment group of the AMG 334 20130255 study (AMG 334 70 mg if the max dose for a subject is 70 mg, AMG 334 140 mg if the max dose for a subject is 140 mg), and study visit using the efficacy analysis set.

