7.2 Efficacy Analysis Set

The Efficacy Analysis Set (EAS) includes subjects who were enrolled and received at least one dose of IP and **had at least one change from baseline measurement in monthly migraine day** in study 20130255. **Subjects will be analyzed according to their randomized treatment group in the parent study 20120295 and the first dose received in the 20130255 OLE study, irrespective if a subject received only AMG 334 70 mg, 140 mg or both 70 mg and 140 mg in the 20130255 OLE study.**

Treatment group identifiers will be as follows:

- **Placebo / AMG 334 70 mg**
- **Placebo / AMG 334 140 mg**
- **AMG 334 70 mg / 70 mg**
- **AMG 334 70 mg / 140 mg**
- **AMG 334 140 mg / 70 mg**
- **AMG 334 140 mg / 140 mg**

Analyses for efficacy endpoints and patient reported outcomes (PROs) will utilize this analysis set except C-SSRS and MPFID.

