9.3 Handling of Missing and Incomplete Data

Subjects may miss specific data points for a variety of causes. In general, data could be missing due to a subject's early withdrawal from study, a missed visit, or inability to evaluate an endpoint at a particular point in time. For this study, most of the efficacy endpoint will be collected via eDiary and subjects could miss entering several days of data **in between exposures to IP**. The general procedures outlined below describe what will be done when a data point is missing.

Missing eDiary data in the calculation of monthly measurements about subjects' migraine and non-migraine headaches will be handled **using method below**. Unless otherwise specified, all the final analysis and sensitivity analysis will use monthly measurements calculated as follows:

1. **For monthly intervals with ≥ 14 days of eDiary days (days subjects use eDiary and including retrospective eDiary days) in each interval:**
 - a) Monthly frequency measurements (including migraine days, headache days, migraine attacks, cumulative hours of migraine headaches, cumulative hours of migraine headaches with severe pain, acute medication use, etc.) will be

prorated to 28-day equivalents. **Prorated result does not need to be rounded.**

- b) Monthly average severity of migraine pain, migraine related symptoms, **physical impairment scores and impact on everyday activities scores as measured by MPFID** and monthly average scale of migraine interference with daily activity will be calculated as the average of observed scores.
2. **For monthly intervals with < 14 days of eDiary use (including retrospective eDiary days)**, all monthly measurement will be set as missing and will be handled as described in [Section 9.3.2](#)

An information day is a calendar day which is either an eDiary day or headache day and will be used toward headache day proration. The eDiary days will be used toward migraine day proration and medication use day proration.

Missing PROs (MSQ, MIDAS) collected at office visit at certain assessment will not be imputed.

Missing safety endpoints will not be imputed. **Missing day portion of AE start time will be imputed based on [Section 9.3.1](#).**

Missing pharmacokinetic and antibody data will not be imputed.

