10.1 General Principles

The final analysis for the entire study including open-label treatment phase and safety follow-up phase will be performed at the end of study.

All subjects who have enrolled and received at least one dose of AMG 334 in the study will be included in the data analysis.

For the purpose of secondary and exploratory efficacy endpoints in the 20130255 OLE study, the primary baseline is the 20120295 parent study baseline **(from the first day subject used eDiary in baseline at week -4 study visit through the day prior to**

study day 1). However, change from the parent study month 3 data may also be evaluated.

Efficacy endpoints will be summarized based on their randomized treatment group assignment in the parent study 20120295 **and the first dose received in the 20130255 OLE study.**

Summary descriptive statistics by each treatment group will be tabulated at each visit. For continuous endpoints number of observations, mean, median, standard deviation, first and third quartiles, minimum and maximum, and a two-sided 95% confidence intervals of the mean (except for safety laboratory analyses) will be included for descriptive statistics. For categorical and ordinal endpoints, the summaries will contain the number and percentage of subjects falling into each category.

No formal statistical tests will be performed. Missing values for safety endpoints will not be imputed.

The full analysis set will be utilized to summarize subject disposition of all enrolled subjects, demographic data, and baseline disease characteristics. The efficacy analysis set will be utilized to analyze efficacy endpoints. The SAS will be used to analyze safety endpoints, **which is the same as the FAS. The PRO analysis set will be used for the PRO substudy (ie evaluation of MPFID).**

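### MSQ and MIDAS summaries exclude subjects who lack a diary-based migraine-day change, and the protocol names two different sets for efficacy

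*Protocol*

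**What the plan says.** Two adjacent protocol sections give different populations for efficacy.

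- Protocol 10.4.1 lists efficacy among the items run on the full analysis set: "The full analysis set will be utilized to tabulate subject disposition of all enrolled subjects, the demographic data, baseline disease characteristics, efficacy, and safety endpoints". Protocol 10.1.2 defines that set without any diary condition: "The full analysis set (FAS) includes all subjects who were enrolled in the study and received at least one dose of investigational product".
- Protocol 10.4.2 says the efficacy summaries are given by treatment group "and study visit using the efficacy analysis set". Section 10.1.2 defines the full, PRO-substudy and home-use sets, but no efficacy set.

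The SAP uses the efficacy set and supplies the missing definition. Under SAP 7.2 a subject must be enrolled and dosed, and must also have "had at least one change from baseline measurement in monthly migraine day". The same section sets its reach: "Analyses for efficacy endpoints and patient reported outcomes (PROs) will utilize this analysis set except C-SSRS and MPFID". SAP 10.1 repeats the choice: "The efficacy analysis set will be utilized to analyze efficacy endpoints". MSQ and MIDAS are therefore tabulated on this set.

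MPFID is treated differently. SAP 7.4 gives it a set of its own, defined by having at least one monthly MPFID score.

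SAP Section 11, which records changes from the protocol, covers the grouping by first dose and the omission of bed days and missed work or school days. It does not mention the analysis set for efficacy.

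**The concern.** An entry condition based on having a migraine-day change does no harm to the migraine-day tables, because a subject without any change value adds nothing to an observed-data summary. It does matter for an instrument that is collected separately. MSQ and MIDAS are questionnaires completed at clinic visits. Their availability is not defined by how many days the subject filled in the diary. Applying the migraine-day condition to them removes scores that were observed, because a different post-baseline endpoint is missing.

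What is at stake is the completeness of the quality-of-life and disability tables and a clear statement of whom they describe. A reader of protocol 10.4.1 would expect every dosed subject with a score to be counted. A reader of SAP Section 11 would not learn that the SAP had to choose between two protocol statements.

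**Working it through.** The plan gives no figure on this point to reproduce, so the check is textual, followed by an illustration of size.

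**1. What it takes to enter the efficacy set.** SAP 6.6 sets a change to missing when either the baseline or the post-baseline value is missing. SAP 9.3 says that, for an interval with fewer than 14 eDiary days, "all monthly measurement will be set as missing". Protocol 7.2.1.10 and SAP 6.1.2 collect daily diary data in six intervals: months 1, 2, 3, 6, 10 and 13. Entry therefore needs a usable migraine-day baseline and at least one of these intervals with 14 or more eDiary days.

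**2. Whether MSQ and MIDAS need the same data.** They do not.
- Protocol 7.2.4 says of these two instruments: "The subject will complete these PROs while in the clinic, using the eDiary". The device is shared, but no daily entries are required.
- SAP 6.4 maps PROs from office visits to visit windows, and SAP 9.3 leaves missing MSQ and MIDAS values unimputed. Neither section sets a minimum number of diary days for them.
- Protocol Table 1 schedules MSQ at every monthly visit from week 4, and MIDAS at weeks 12, 24, 36 and 52/early termination. Of the 13 MSQ visits from week 4 to week 52, six close a diary interval. The other 13 − 6 = 7 (months 4, 5, 7, 8, 9, 11, 12) close a month with no daily diary. So does the week 36 MIDAS.

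**3. Who is left out despite having scores.**
- Subjects below 14 eDiary days in every collected interval.
- Subjects without a usable migraine-day baseline. How often this occurs depends on the parent-study SAP, to which SAP 9.3.2 refers.
- Subjects who leave before 14 diary days but attend an early-termination visit. The week 4 window in SAP 6.4 is study days 2 to 43, so an MSQ score from such a visit would otherwise be tabulated at week 4.

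**4. How hard it is to fail.** For illustration, assume 28-day intervals, independent days and a constant daily completion probability p. The chance of failing one interval is q = P(Binomial(28, p) ≤ 13). The chance of failing all six, for a subject who stays throughout, is q^6.

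| p | q | q^6 |
|---|---|---|
| 0.4 | 0.813 | 0.289 |
| 0.5 | 0.425 | 0.0059 |
| 0.6 | 0.102 | about 0.000001 |

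Among subjects who stay, only near-total non-users of the diary are at real risk. Those who leave after one interval have a single chance, so their risk is q itself, about 10% at p = 0.6.

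**5. Size.** Let f be the share of the maximum 651 subjects who fail the condition. The documents give no value for f, so a range is assumed. The subjects lost number 651 × f:
- f = 0.5%: 3.3, about 3
- f = 1%: 6.5, about 7
- f = 2%: 13.0, about 13
- f = 3%: 19.5, about 20
- f = 5%: 32.6, about 33

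The mean over all subjects equals the mean over included subjects plus f × d, where d is the excluded mean minus the included mean. If d is 0.5 SD in absolute size, the shift is 0.005 × 0.5 = 0.0025 SD to 0.05 × 0.5 = 0.025 SD. If d is 1 SD, it is 0.005 to 0.05 SD. These are upper bounds at any one visit, because they treat every excluded subject as having a score there.

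**The case against.** The strongest reply is that the SAP follows the protocol. Section 10.4.2 is the dedicated efficacy section and names the efficacy set, whereas 10.4.1 is a general sentence covering disposition and safety as well. This stands to the extent that the SAP cannot simply be called a departure from the protocol: it took one of two protocol statements and defined a term left undefined. The conflict between the two sections, and the silence of SAP Section 11, remain.

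The bar is also low. One interval of six is enough, and retrospective eDiary days count. Entrants have completed the parent double-blind phase, and exclusion criterion 209 screens out those unlikely to complete eDiary items. This stands too, and it is why few exclusions are expected.

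Finally, MSQ and MIDAS are completed on the subject's own eDiary, so a subject who neglects the diary may also lack these scores. That is plausible and would reduce the loss further. It gives no reason to discard the scores that do exist.

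A reader might infer more than the documents support:
- **That partial diary non-compliance excludes subjects.** It does not; one usable interval admits the subject to all tables.
- **That the MSQ and MIDAS results are made to look favourable.** Nothing in the documents shows that the excluded subjects score worse. The direction is unknown.
- **That about a year of data is lost for each very early leaver.** A subject who leaves before 14 diary days has at most an early-termination record, and is absent from later visits under either set.
- **That PROMIS has the same problem.** PROMIS is collected weekly within the same diary windows, so a subject with no usable interval probably has little PROMIS data to lose.

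**Conclusion.** The point holds and is minor. Protocol 10.4.1 and 10.4.2 name different efficacy sets, one of them undefined in the protocol. The SAP definition then excludes observed MSQ and MIDAS scores on the strength of an endpoint unrelated to how those scores are collected. Neither document explains why, and MPFID already has a set based on its own data.

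The expected effect is small: about 3 to 33 of 651 subjects, and at most about 0.05 SD in a mean, if 0.5% to 5% of subjects fail the condition and differ from the rest by up to 1 SD. Both ranges are assumptions. Shares within the six efficacy treatment groups could be higher or lower, and the group sizes are not given.

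MSQ and MIDAS are exploratory and summarised descriptively without testing. The diary-derived endpoints, which include all the secondary efficacy endpoints of the main study, are unaffected. So is the primary endpoint, which uses the safety set that SAP 7.3 equates with the full analysis set. No study conclusion depends on this.

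**What to change.** - In SAP 7.2, limit the migraine-day-change condition to diary-derived endpoints. PROMIS and the other measures collected in the diary windows can stay on that set.
- Analyse MSQ and MIDAS on dosed subjects who have a baseline and at least one post-baseline value of the instrument concerned, as SAP 7.4 already does in kind for MPFID.
- Define the efficacy set in protocol 10.1.2, and make 10.4.1 and 10.4.2 name the same set.
- Add a line to SAP Section 11 recording which set was chosen for efficacy and for the clinic-completed questionnaires.

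The cost is wording and one filter change in the MSQ and MIDAS programs. No new data are needed. The drawback is that denominators will differ slightly between these tables and the diary tables, which a footnote can explain.

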10.4.2 Efficacy Endpoint

Descriptive summaries on efficacy endpoints will be provided by treatment group of the AMG 334 20120295 parent study (ie, AMG 334 70 mg, AMG 334 140 mg), treatment group of the AMG 334 20130255 study (AMG 334 70 mg if the max dose for a subject is 70 mg, AMG 334 140 mg if the max dose for a subject is 140 mg), and study visit using the efficacy analysis set.

10.4.3 Safety Endpoints

For safety endpoints, all enrolled subjects who received at least one dose of investigational product (ie, safety analysis set) will be analyzed based on the maximum actual treatment dose received using safety analysis set.

The Medical Dictionary for Regulatory Activities (MedDRA) version 16 or later will be used to code all adverse events.

The exposure-adjusted subject incidence of all treatment-emergent adverse events will be tabulated by system organ class and preferred term.

Overall summary table of all treatment-emergent adverse events, serious, fatal, leading to withdrawal from investigational products, and treatment-related adverse events will be provided. Tables of fatal adverse events, serious adverse events, and adverse events leading to withdrawal from investigational product will also be provided by system organ class and preferred term.

Treatment-emergent adverse events and serious adverse events will be tabulated by preferred term in descending order of frequency.

Subject incidence of adverse events, serious adverse events, and ADEs will be summarized by system organ class and preferred term for subjects enrolled in the CHU substudy.

Shift tables based on CTCAE grade relative to baseline will be tabulated by treatment group for selected laboratory analytes.

The analyses of vital signs (systolic blood pressure, diastolic blood pressure, heart rate, temperature, weight) will include summary statistics of change from baseline measure over time by treatment group.

The ECG measurements from this clinical study will be performed as per standard of care for routine safety monitoring, rather than for purposes of assessment of potential QTc effect. Since these evaluations may not necessarily be performed under the rigorous conditions expected to lead to meaningful evaluation of QTc data, summaries and statistical analyses of ECG measurements are not planned, and these data would not be expected to be useful for meta-analysis with data from other studies.

The incidence and percentage of subjects who develop anti-AMG 334 antibodies (binding and if positive, neutralizing) at any time will be tabulated by treatment group.

The analysis of subject-reported outcome of attempted full-dose administration at each of day 29 and day 57 as collected in the CHU substudy will include calculating the proportion of each of the subject reported outcomes of attempted full-dose administration at each of weeks 4 and 8. For all subjects who have not discontinued IP, a subject report of full dose administration will be considered a “yes” response, and a subject report of partial or no dose administered will be considered a “no” response. The proportion of each possible pattern of responses across the two visits will also be estimated. Ninety-five percent confidence intervals will be provided for each group and the difference in proportions between the groups.

10.4.4 Others

Descriptive summaries of the primary and secondary endpoints may be provided by subgroups stated in [Section 10.1.3](#).

11. REGULATORY OBLIGATIONS

11.1 Informed Consent

An initial sample informed consent form is provided for the investigator to prepare the informed consent document to be used at his or her site. Updates to the template are to be communicated formally in writing from the Amgen Clinical Study Manager to the investigator. The written informed consent document is to be prepared in the language(s) of the potential patient population.

Before a subject's participation in the clinical study, the investigator is responsible for obtaining written informed consent from the subject after adequate explanation of the aims, methods, anticipated benefits, and potential hazards of the study and before any protocol-specific screening procedures or any investigational products are administered.

The investigator is also responsible for asking the subject if the subject has a primary care physician and if the subject agrees to have his/her primary care physician informed of the subject's participation in the clinical study. If the subject agrees to such notification, the investigator is to inform the subject's primary care physician of the subject's participation in the clinical study. If the subject does not have a primary care physician and the investigator will be acting in that capacity, the investigator is to document such in the subject's medical record. The acquisition of informed consent and the subject's agreement or refusal of his/her notification of the primary care physician is to be documented in the subject's medical records, and the informed consent form is to be signed and personally dated by the subject and by the person who conducted the informed consent discussion. The original signed informed consent form is to be retained in accordance with institutional policy, and a copy of the signed consent form is to be provided to the subject.

